4 STUDY POPULATION

4.0.1 Overview: Target Population

20 patients with Syn-ILD will be enrolled. Patients must have active ILD associated with anti-synthetase syndrome (a subset of myositis) that is being given SOC treatment for ILD. It will be randomized for patients to receive the drug vs. placebo as weekly SQ injections with their SOC treatment for 24 weeks. Patients could have refractory disease with flare up or new onset disease. They may or may not have active myositis (PM/DM). Given our current cohort of Syn-ILD

patients, we expect enrollment to be completed within 15 months. We anticipate the continued participation of all subjects in open label extension phase (Phase II).

4.1 Inclusion Criteria

Patients will be included in the trial based on the following criteria:

1. Age \geq 18 years.
2. Anti-synthetase syndrome defined as the patient possessing 1 antisynthetase autoantibody (Jo-1, PL-12, PL-7, KS, OJ, EJ, Zo) in the presence of autoimmune ILD.
3. ILD defined by radiographic (HRCT chest) findings of reticulation, honeycombing or ground glass opacities (GGO) without another plausible explanation. HRCT chest defining ILD for inclusion criteria, should be within last 1 year done as SOC.
4. Active ILD (see Section 4.2).
5. Baseline FVC % :
6. a) FVC <80% OR b) FVC 80-100% with \geq 10% decline in FVC in last 12 months as minimal threshold of ILD severity (PFT done within last 3 months is acceptable for inclusion criteria determination).
7. SOC immunosuppressive therapy (IS) therapy:
 - a. Steroids (prednisone or other forms of steroid in equivalent doses) OR one of the other immunosuppressive agent (either Mycophenolate (MMF) or Azathioprine) OR a combination of steroid and an immunosuppressive agent. MMF (maximum of 3 gm/day) or azathioprine (maximum of 200 mg/day). Goal is to start the trial drug (or placebo) soon after starting SOC (MMF/AZA/Steroids) and their doses are stable. Note that patients on steroids alone as well as not on steroids can be enrolled in the trial as well.
 - b. Desired dose of the SOC therapy should be reached 4 weeks prior to first study visit (Visit 1). No dose changes are allowed 4 weeks prior to first study visit.
 - c. Dose of concomitant therapy (SOC) cannot be changed during the 24 weeks of the trial unless safety/toxicity issues supervene.
 - d. If on steroid, the steroid dose must be stable for 2 weeks prior to Visit 1.
8. No other concomitant IS medications including methotrexate, cyclosporine, IVIG, tacrolimus, cyclophosphamide or tofacitinib.
9. No concomitant biologic agents (i.e. rituximab, anti-TNF agents, tocilizumab).
10. Additional IS therapy: Patient cannot begin any new IS therapy or new steroid taper for the 24-week study period, except if severe clinical worsening (flare up) of the disease requiring rescue therapy occurs (i.e. documentation of worsening of PFT/HRCT **and** patient and physician determination of worsening). See section of rescue medication below for details.
11. If the enrolling physician is planning to discontinue current IS agent or steroid before clinical trial, then following washout period is required prior to Visit 1.

Medication	Washout Period
------------	----------------

Methotrexate	4 weeks
Other IS agent (e.g. azathioprine, cyclosporine, tacrolimus, leflunomide, mycophenolate mofetil)	4 weeks
IVIg or cyclophosphamide	3 months
Rituximab	6 months
infliximab or adalimumab	8 weeks
Glucocorticoids	2 weeks
Etanercept	2 weeks
Anakinra	1 week
Pirfenidone	4 weeks

12. Men and women of reproductive potential must agree to use an acceptable method of birth control during the trial period.
13. Subject has provided written informed consent.

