7.0 OBSERVATIONS PER VISIT

7.1 Screening Visit (Visit 0)

The following assessments will be performed during the Screening Visit:

Screening Visit (Visit 0)

1. Obtain informed consent from the subject.
2. Review concomitant medications for defined study washout and restriction of immunosuppressive (IS) medications.
3. Urine Pregnancy (if applicable) for all females of childbearing potential.
4. Obtain safety screening tests to include: serologies for Hepatitis B (Hep B surface Ab, surface antigen and core antibody), Hepatitis C (Qualitative HCV antibody) and tuberculosis (Quantiferon TB Gold) if a negative result was not obtained **within the last year**. If Quantiferon gold is non-interpretable or cannot be done, then skin PPD test for tuberculosis should be done.
5. Pulmonary Function Test (PFT) with DLCO should be obtained.
6. If a High-Resolution Computed Tomography (HRCT) chest has been completed as part of the patients' standard of care the results should be recorded on the HRCT chest ILD Assessment Form.
7. Brief Evaluation (history/physical)
8. Obtain and record vital sign measurements.
9. Complete screening evaluation, demographics and screening criteria assessments.

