7.2 Other Study Visits

Study Visits 1, 2 and 3 (Weeks 0, 12, and 24)

Subjects who are eligible will visit the study site and enter the randomized treatment phase after randomization. Visit 1 should take place within 21 days after the Screening Visit.

All eligible subjects will receive their first injection of either abatacept 125mg SQ injection or placebo as per randomization at Visit 1. The following assessments will be performed:

The following research procedures will be conducted at Visits 1, 2 and 3 unless otherwise noted:

- Review concomitant medications
- A urine pregnancy (if applicable) will be performed for all females with child bearing potential.
- Site pharmacist will randomize subject to receive either study drug or placebo.
- Perform and record functional test (6 minute walk distance test - 6MWD)
- Administer patient questionnaires to include: dyspnea, patient global, SF-36 and health assessment questionnaires and patient assessment of change
- Site Investigator to perform Manual Muscle Test (MMT-8)
- Site Investigator to complete MDAAT, brief physical exam and physician assessment of change
- Obtain safety screening tests to include: creatine kinase(CK), aldolase, complete blood count with differential, serum creatinine and liver function tests
- Obtain research repository blood per study schema (Appendix A)
- Instruct the subject on how and when to use the FitBit One ® device. Patient will wear FitBit device for 7 consecutive days one a month for 6 months. Refer to Manual of Operations for specific procedures for syncing the device. - **visit 1 only**
- A pulmonary function test will be performed at **visits 2 and 3 only**
- Assess and record adverse events (if applicable) – **visits 2 and 3 only**
- If a High-Resolution Computed Tomography (HRCT) chest has been completed as part of the patient standard of care, the research coordinator will obtain and record the results of this test for research purposes at **visit 1 and 3 only**. A CD of HRCT chest (at baseline and follow up) should be mailed to coordinating center for centralized evaluation in future.

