11.2 Reporting of Serious Adverse Events Associated with Abatacept

Immediate Reporting Requirements:

Non-serious AEs and SAEs whether or not related to the BMS product associated to this study, pregnancies, AEs associated with maternal exposure, and pregnancy outcomes ascertained in the study must be reported individually in the time frames noted below. All AEs collected will also be reported in aggregate in the final study report. Any component of a study endpoint that is considered related to study therapy (e.g., death is an endpoint, if death occurred due to anaphylaxis, anaphylaxis must be reported) should be reported as an SAE.

Serious Adverse Event Collection and Reporting

- All Serious Adverse Events (SAEs) that occur following the subject's written consent to participate in the study through 30 days of discontinuation of dosing must be reported to BMS Worldwide Safety. If applicable, SAEs must be collected that relate to any later protocol-specified procedure (e.g., a follow-up skin biopsy).
- The MedWatch form 3500A will be used to report SAEs. The form will be reviewed and approved by BMS. The BMS protocol ID number must be included on whatever form is submitted by the Sponsor/Investigator. The form can be accessed at: <http://www.accessdata.fda.gov/scripts/medwatch/>.
- Following the subject's written consent to participate in the study, all SAEs, whether related or not related to study drug, are collected, including those thought to be associated with protocol-specified procedures. The investigator should report any SAE occurring after these time periods that is believed to be related to study drug or protocol-specified procedure. For drugs with potential for delayed SAEs (e.g., delayed excretion of the parent or active metabolites), a longer follow-up period may be warranted to allow collection of these SAEs Laboratory tests, and other assessments.
- For studies with long-term follow-up periods in which safety data are being reported, include the timing of SAE collection.

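### Six of the nine washout periods in 4.1 item 11 do not fit between consent at Visit 0 and Visit 1, so a longer washout undertaken to enter the trial starts before consent and outside SAE collection

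*Combined protocol and SAP*

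**What the plan says.** Four parts of the combined protocol and SAP bear on this.

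- **Washout (4.1 item 11).** Where the enrolling physician is "planning to discontinue current IS agent or steroid before clinical trial, then following washout period is required prior to Visit 1", a table of nine rows gives the periods, all counted back from Visit 1. Examples are "Methotrexate 4 weeks" and "IVIg or cyclophosphamide 3 months". The 4-week row for other agents reads "Other IS agent (e.g. azathioprine, cyclosporine, tacrolimus, leflunomide, mycophenolate mofetil". Items 8 and 9 bar other concomitant immunosuppressants and biologics, naming methotrexate, cyclosporine, tacrolimus, IVIG, cyclophosphamide, rituximab and anti-TNF agents among them.
- **Consent (7.1).** The first procedure at Visit 0 is "Obtain informed consent from the subject". The second is "Review concomitant medications for defined study washout and restriction of immunosuppressive (IS) medications". No earlier consent contact is described.
- **Interval to first dose (7.2, Appendix B, 10.1).** Section 7.2 states "Visit 1 should take place within 21 days after the Screening Visit", and the flow chart gives the same 0 to 21 days with no exception. Section 10.1 sets two weeks before first treatment for several screening evaluations unless otherwise specified.
- **Safety collection (11.2).** Serious adverse events (SAEs) that occur after the subject's "written consent to participate in the study through 30 days of discontinuation of dosing must be reported to BMS Worldwide Safety". Non-serious events are collected from the start of study drug.

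**The concern.** Item 11 looks forward. It concerns a current drug, a planned stop, and the physician who is enrolling the patient. A patient taking a barred agent must come off it to qualify. If the washout is longer than the time allowed between consent and Visit 1, a site that follows the schedule has to start the washout before the patient has signed.

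Two things are at stake. The first is consent to a treatment change made for research purposes. The second is safety data. Section 6.2 acknowledges that restricting therapy carries a risk of deterioration, and section 11.2 asks investigators to note in the SAE narrative when an event may be due to withdrawal of earlier treatment. An interstitial lung disease (ILD) flare in the pre-consent part of a washout is the kind of event those passages anticipate, yet it falls before SAE collection begins.

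The situation is not remote. Refractory patients are eligible (3.1.1), and section 1.2 describes tacrolimus and cyclosporine as effective in refractory disease. Both are barred and both fall in a 4-week row.

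**Working it through.** **Inputs.** Washout periods are from the table in 4.1 item 11. The Visit 0 to Visit 1 limit is 21 days (7.2, Appendix B). The two-week limit in 10.1 is used as a second case, on the assumption that consent is taken at the same visit as those evaluations. Months are taken as calendar months: 3 months = 89 to 92 days, 6 months = 181 to 184 days. There is no power or sample-size figure to reproduce, because the check is calendar arithmetic only.

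**Formula.** Minimum days off drug before consent = max(0, washout − window).

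| Row | Washout (days) | 21-day window | 14-day window |
|---|---|---|---|
| Methotrexate | 28 | 28 − 21 = 7 | 28 − 14 = 14 |
| Other immunosuppressants | 28 | 7 | 14 |
| Pirfenidone | 28 | 7 | 14 |
| Infliximab or adalimumab | 56 | 56 − 21 = 35 | 56 − 14 = 42 |
| IVIg or cyclophosphamide | 89–92 | 68–71 | 75–78 |
| Rituximab | 181–184 | 160–163 | 167–170 |
| Glucocorticoids | 14 | 0 | 0 |
| Etanercept | 14 | 0 | 0 |
| Anakinra | 7 | 0 | 0 |

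**Result.** Six of nine rows exceed the window and three fit, whichever window is used.

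**Which rows carry weight.**

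- *4-week rows.* Methotrexate, tacrolimus and cyclosporine are barred by item 8, so entry requires a stop. Azathioprine and mycophenolate are permitted standard care, so the trial forces a stop only for a patient on both. Pirfenidone is not among the agents that items 8 and 9 name.
- *8-week row.* Infliximab and adalimumab are anti-TNF agents, barred by item 9.
- *3- and 6-month rows.* Section 3.1.1 defines active ILD by onset, or by a treatment change for worsening, within the last 3 months. A patient who qualified and then began a 6-month washout could be outside both windows by Visit 1. These rows more plausibly describe past exposure.

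**Safety collection against this timeline.** Days before consent have no SAE collection and no non-serious collection. Days from consent to first dose have SAE collection only. Section 11.1 mentions collecting non-serious events from a lead-in or observational baseline period, but the plan defines no such period.

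**The case against.** The strongest reply is that item 11 does not say the stop is made for the trial. It is conditional, and the definition of active ILD in 3.1.1 already expects recent treatment changes in ordinary care. On that reading, the Visit 0 medication check only looks back at what has happened. A stop made for independent clinical reasons needs no research consent. This stands and limits the point to stops made in order to enrol, but item 11 is not confined to the other kind.

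Several stronger readings are tempting, and the documents do not support them:

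- *All immunosuppression stopped for the trial must be stopped before consent.* Glucocorticoids, etanercept and anakinra can be washed out after consent.
- *Patients are left untreated.* Item 7 requires permitted standard care, with its dose reached 4 weeks before Visit 1.
- *The 21-day limit is absolute.* Section 7.2 words it as *should*. A site could consent first and exceed the window, but nothing tells it to, and Appendix B shows no exception.
- *Patients typically spend more than five months off drug before consent.* That is the arithmetic for the rituximab row, not a likely enrolment path.

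It can also be said that nothing forbids earlier consent, and that the consent form and Manual of Operations are not available to this review. If consent were taken earlier, 11.2 would start SAE collection at that point. That is fair, and it is why the remedy is small. The protocol as written still lists consent only at Visit 0.

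**Conclusion.** The conflict is real but narrower than the table first suggests. For a stop made in order to enter the trial, six of nine washout rows cannot be completed between the only described consent step and Visit 1. The practical size is at least 7 days before consent for barred agents in the 4-week rows, and at least 35 days for infliximab or adalimumab. The two-week limit in 10.1, if it governs the consent visit, makes these 14 and 42 days.

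This rests on three assumptions: consent is taken at Visit 0 as listed, the 21-day window is followed, and the stop is trial-directed. The documents do not show how many patients this would affect or that sites would handle it differently. The finding concerns patient protection and completeness of safety data. It does not touch the sample size or the primary analysis, and it does not question any washout length.

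**What to change.** Reconcile 4.1 item 11, 7.1, 7.2, 10.1, 11.2 and Appendix B so that written consent and SAE collection come before any discontinuation made for the trial. One way is to allow consent ahead of Visit 0 and run the 21-day window from the Visit 0 tests rather than from consent. SAE collection would then follow from 11.2 without new rules. The same edit should state whether non-serious events are collected during such a washout, since at present they start only with study drug, and should say how the two-week limit in 10.1 relates to the 21 days.

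The cost is a few lines of text, earlier signatures, possibly one extra contact for some patients, and a somewhat longer SAE collection period for them. No washout length or treatment rule is proposed or changed.

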3.4 End of Study

As described above, the end of the study (closing visit) is week 24 for Phase I. An optional open label phase (Phase II) with 2 additional visits 3 months and 6 months after the closing visit at week 24 have been added to assess durability of ABT response and safety. This follow-up phase will assess durability, long term response and safety in patients who were in the active treatment arm while allowing the placebo arm to receive active study drug.

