4.2 Exclusion Criteria

A patient will be excluded if any of the following Exclusion Criteria are met:

1. Severe end stage lung disease:
 - a. FVC $\leq 30\%$ *or* FEV1 $\leq 30\%$ *or*
 - b. Requirement of high O₂ requirement ≥ 6 L/min at rest for >1 month before the study enrollment *or*
 - c. Listed for lung transplantation *or*
 - d. PI feels that ILD is severe and end stage fibrosis is such that there is low potential for improvement with any disease modifying intervention.
2. Subjects under the age of 18.
3. Known active current or history of recurrent bacterial, viral, fungal, mycobacterial or other infections (including but not limited to tuberculosis and atypical mycobacterial disease, hepatitis B and C, and herpes zoster, but excluding fungal infections of nail beds).
4. Any major episode of infection requiring hospitalization or treatment with IV antibiotics within 4 weeks of screening.
5. Active TB requiring treatment within the previous 3 years. Patients should be screened for latent TB using PPD/or quantiferon gold within last 1 year and, if positive, treated following local practice guidelines prior to initiating ABT. Patients treated for active tuberculosis with no recurrence in 3 years are permitted.
6. Primary or secondary immunodeficiency (history of or currently active) unless related to primary disease under investigation.
7. Pregnant women or nursing (breast feeding) mothers.
8. History of alcohol, drug or chemical abuse within 1 year prior to screening or any medical condition or physical or psychological state that the PI feels would not allow the subject to safely complete the study.
9. Major surgery (including joint surgery) within 8 weeks prior to screening or planned major surgery within 6 months following randomization.
10. Treatment with any other investigational agent within 4 weeks (or 5 half-lives of the investigational drug, whichever is longer) of screening.

11. Previous treatment with the following cell-depleting therapies, including investigational agents or approved therapies: CAMPATH, anti-CD4, anti-CD5, and anti-CD3.
12. Previous treatment with ABT.
13. History of severe allergic or anaphylactic reactions to monoclonal antibodies.
14. Evidence of serious uncontrolled concomitant cardiovascular, nervous system, renal, hepatic, endocrine (include uncontrolled diabetes mellitus) or gastrointestinal disease (including complicated diverticulitis, ulcerative colitis, or Crohn's disease.)

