6.2 Other Risks

Physical Activity Monitor (PAM) Use: There is the possibility of minor skin irritation associated with wearing the PAM device. There may be minor risk of skin irritation from use of the elastic belt if used with the PAM device. Keeping the band clean, dry and loosely fitting will help reduce this risk.

Blood Drawing: Subjects may experience pain, bruising and/or bleeding at the site of the needle insertion for blood drawing. Very rarely an infection may occur at the site. Subjects may also experience dizziness and/or fainting.

Risk of Breach of Confidentiality: Study data and blood specimens collected during the course of this trial will be labeled with a study code and contain no personal subject identifiers that could directly identify the subject and will be stored in a secure location; however there is a chance that a breach of confidentiality will occur and the subject personal or medical health information may be inappropriately distributed.

Data that is transferred from your FitBit One ® device will not contain any identifiable personal information. The data will be stored on a secure network server located in the Department of Medicine, Division of Rheumatology. Study data will be stored in the Rheumatic Disease Management System (RDMS) located at the University of Pittsburgh, Division of Rheumatology which is located on a secure server behind a network firewall. There is the possibility that if the results of the research studies involving biologic samples or genetic material were to become known this information could affect the subjects ability to be insured or employed, reputation, and future plans for children, or family relationships. Although every reasonable effort has been taken,

confidentiality during Internet communication activities cannot be guaranteed and it is possible that additional information beyond that collected for research purposes may be captured and used by others not associated with this study.

Reproductive Risks: The effect of the study drug on the unborn child is unknown.

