9.0 CRITERIA FOR SUBJECT DISCONTINUATION

9.1 Abatacept-Specific Criteria

Subjects who meet the following criteria should be discontinued from the study:

- Anaphylaxis or hypersensitivity reaction or requires an interruption of the study drug because of symptoms of anaphylaxis or hypersensitivity (ABT should be permanently discontinued from these patients)
- If, following initiation of study drug, it is subsequently discovered that a study participant is pregnant or may have been pregnant at the time of study drug administration, including at least 5 half-lives administration, the study drug will be permanently discontinued.

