- Admission encountered for another life circumstance that carries no bearing on health status and requires no medical/surgical intervention (e.g., lack of housing, economic inadequacy, caregiver respite, family circumstances, administrative reasons).
- Admission for administration of subsequent anti-cancer therapy in the absence of any other SAEs (applies to oncology protocols).

Laboratory Test Abnormalities

All laboratory test results captured as part of the study should be recorded following institutional procedures. Test results that constitute SAEs should be documented and reported as such. The following laboratory abnormalities should be documented and reported appropriately:

- Any laboratory test result that is clinically significant or meets the definition of an SAE
- Any laboratory abnormality that required the participant to have study drug discontinued or interrupted
- Any laboratory abnormality that required the subject to receive specific corrective therapy.

It is expected that wherever possible, the clinical rather than laboratory term would be used by the reporting investigator (e.g., anemia versus low hemoglobin value).

Potential Drug Induced Liver Injury (DILI)

Wherever possible, timely confirmation of initial liver-related laboratory abnormalities should occur prior to the reporting of a potential DILI event. All occurrences of potential DILIs, meeting the defined criteria, must be reported as SAEs.

Potential drug induced liver injury is defined as:

- 1) AT (ALT or AST) elevation > 3 times upper limit of normal (ULN) AND
- 2) Total bilirubin > 2 times ULN, without initial findings of cholestasis (elevated serum alkaline phosphatase), AND
- 3) No other immediately apparent possible causes of AT elevation and hyperbilirubinemia, including, but not limited to, active myositis with elevated CK, viral hepatitis, pre-existing chronic or acute liver disease, or the administration of other drug(s) known to be hepatotoxic.

Pregnancy

If, following initiation of the investigational product, it is subsequently discovered that a study participant is pregnant or may have been pregnant at the time of investigational product exposure, including at least 5 half-lives after product administration, the investigational product will be permanently discontinued in an appropriate manner (e.g., dose tapering if necessary for participant).

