The investigator must immediately notify [contact] of this event via the Pregnancy Surveillance Form in accordance with SAE reporting procedures.

Protocol-required procedures for study discontinuation and follow-up must be performed on the participant.

Follow-up information regarding the course of the pregnancy, including perinatal and neonatal outcome and, where applicable, offspring information must be reported on the Pregnancy Surveillance Form [provided upon request from BMS]

Any pregnancy that occurs in a female partner of a male study participant should be reported to BMS. Information on this pregnancy will be collected on the Pregnancy Surveillance Form. In order for Sponsor or designee to collect any pregnancy surveillance information from the female partner, the female partner must sign an informed consent form for disclosure of this information.

Overdose

An overdose is defined as the accidental or intentional administration of any dose of a product that is considered both excessive and medically important. All occurrences of overdose must be reported as an SAE.

Other Safety Considerations

Any significant worsening noted during interim or final physical examinations, electrocardiograms, X-rays, and any other potential safety assessments, whether or not these procedures are required by the protocol, should also be recorded as a non-serious or serious AE, as appropriate, and reported accordingly.

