SAEs, whether related or not related to study drug, as well as pregnancies, must be reported to BMS within 24 hours. SAEs must be recorded on the MedWatch form; pregnancies must be reported on a Pregnancy Surveillance Form.

- An SAE report should be completed for any event where doubt exists regarding its seriousness.
- For studies with long-term follow-up periods in which safety data are being reported, include the timing of SAE collection in the protocol.
- If the investigator believes that an SAE is not related to study drug, but is potentially related to the conditions of the study (such as withdrawal of previous therapy or a complication of a study procedure), the relationship should be specified in the narrative section of the SAE Report Form.
- If only limited information is initially available, follow-up reports are required. (Note: Follow-up SAE reports should include the same investigator term(s) initially reported.)

If an ongoing SAE changes in its intensity or relationship to study drug or if new information becomes available, a follow-up SAE report should be sent within 24 hours to BMS (or designee) using the same procedure used for transmitting the initial SAE report. All SAEs should be followed to resolution or stabilization.

Non-serious Adverse Event Collection and Reporting

The collection of non-serious AE information should begin at initiation of study drug. All non-serious adverse events (not only those deemed to be treatment-related) should be collected continuously during the treatment period and for a minimum of 30 days following the last dose of study treatment.

All non-serious AEs must be reported by confirmed fax transmission or reported via electronic mail to:

Non-serious AE Email Address: [contact]

Non-serious AE [contact]

Non-serious AEs should be followed to resolution or stabilization, or reported as SAEs if they become serious. Follow-up is also required for non-serious AEs that cause interruption or discontinuation of the BMS product associated with this study and for those present at the end of the study, as appropriate.

MedWatch 3500A Reporting Guidelines

In addition to completing appropriate patient demographic and suspect medication information, the report should include the following information within the Event Description (section 5) of the MedWatch 3500A form:

- Treatment regimen (dosing frequency, combination therapy)
- Protocol description (and number, if assigned)

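### The birth-control rule has no stated end after the last dose, although the protocol treats a pregnancy as exposed for at least 5 half-lives after dosing

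*Combined protocol and SAP*

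**What the plan says.** **Contraception.** Section 4.1, item 12, reads: "Men and women of reproductive potential must agree to use an acceptable method of birth control during the trial period". It covers both sexes. It does not say when the period ends or mention the last dose.

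**End of the trial.** Section 3.4 says that "the end of the study (closing visit) is week 24 for Phase I", followed by an optional open-label phase. Section 7.3 places the open-label visits at weeks 36 and 48. None of these sections ties its end point to the term used in item 12.

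**Exposure window.** The pregnancy text in section 11.1 deals with a participant found to be pregnant, or possibly pregnant, at the time of exposure, "including at least 5 half-lives after product administration". It requires permanent discontinuation and immediate notification. Section 9.1 carries a parallel sentence with the word *after* missing: "including at least 5 half-lives administration, the study drug will be permanently discontinued". Section 11.1 therefore holds the clear statement.

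**Fetal risk.** Section 6.2 says: "The effect of the study drug on the unborn child is unknown".

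**Follow-up after dosing.** Section 11.2 requires collection of non-serious adverse events "for a minimum of 30 days following the last dose of study treatment". It also requires reporting of serious events through 30 days after dosing stops. Section 11.1 handles pregnancy as a serious event for this purpose and requires "Follow-up information regarding the course of the pregnancy, including perinatal and neonatal outcome" to be reported.

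**The concern.** The protocol accepts that study drug can matter to a pregnancy for some time after the last injection, and it says how long: at least 5 half-lives. Contraception is the measure that prevents such exposure, yet its end point is left open. Nothing in item 12 carries it past the last study contact.

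A participant could comply with item 12, stop birth control at the closing visit, conceive soon afterwards, and come straight under the exposed-pregnancy provisions of section 11.1. Those provisions act after conception and do not prevent exposure. Sites that read the undefined term differently would also give participants different instructions.

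What is at stake is fetal exposure to a drug whose effect the protocol calls unknown. The efficacy comparison is not affected.

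**Working it through.** The plan has no figure of its own to reproduce. The check compares two intervals, both counted from the last dose.

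**Inputs**
- *W*, the exposure window: at least 5 × *h*, where *h* is the half-life in days (section 11.1). The documents do not give *h*.
- *E*, the days from last dose to the end of required birth control. This depends on how item 12 is read.
 - Reading A: the period ends at the closing visit (week 24, or week 48 with open label). Dosing is weekly (section 5.1.1), so the last dose falls about 0 to 7 days before that visit, and *E* = 0 to 7. The same weekly pattern is assumed in both phases. The syringe count in section 7.2 is approximate, and one dose is taken at Visit 1, so it does not fix the date of the last dose more closely.
 - Reading B: the period takes in the 30-day adverse event window (section 11.2), so *E* = 30.

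**Break-even half-life**

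Cover falls short when 5*h* > *E*, that is, when *h* > *E*/5.
- Reading A, *E* = 7: 7/5 = 1.4 days.
- Reading A, *E* = 0: any half-life gives a shortfall.
- Reading B, *E* = 30: 30/5 = 6 days.

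**Illustration under an assumed half-life**

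Take *h* = 7 to 21 days. This range is an assumption, not a document value. Then *W* = 5 × 7 = 35 to 5 × 21 = 105 days, and the shortfall is 5*h* − *E*.

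| Reading | *h* = 7 | *h* = 21 |
|---|---|---|
| A, *E* = 7 | 35 − 7 = 28 days | 105 − 7 = 98 days |
| A, *E* = 0 | 35 − 0 = 35 days | 105 − 0 = 105 days |
| B, *E* = 30 | 35 − 30 = 5 days | 105 − 30 = 75 days |

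The table shows scale only. The break-even values carry the point, because they need no assumed half-life.

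**Who is affected**

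Sections 3.1.1 and 4.0.1 expect all 20 participants to enter open label. On that expectation the gap arises mainly once, after about week 48, with up to 20 people coming off abatacept. The documents do not say how many would be of reproductive potential. Section 4.5.3 keeps participants who stop study drug early in follow-up, so for them item 12 may cover part or all of the window.

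**The case against.** **The 5-half-life text is not a contraception rule.** This is correct. Sections 9.1 and 11.1 govern discontinuation and notification, and a reporting window may reasonably be wider than a contraception period. A reader might infer that the sections contradict each other. They do not, since both can be followed at once. What remains is a mismatch: the protocol states its own view of how long exposure lasts, and the preventive rule does not use it.

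**Participants may already be told a period.** The consent pages were removed before review and the Investigator's Brochure was not supplied. A reader might infer that participants receive no post-dose instruction, but the documents cannot show that. The point is limited to item 12, the eligibility commitment that sites apply.

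**Follow-up does not stop at the closing visit.** A reader might infer from the visit schedule, which shows no contact after the last visit, that a later pregnancy would be learned of only by self-report. The 30-day collection duties in section 11.2, with pregnancy handled as a serious event, rule that out for the first 30 days. It could apply only after day 30.

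**Other post-dose intervals are not yardsticks.** Section 4.2, item 10, sets a washout for other investigational agents ("or 5 half-lives of the investigational drug, whichever is longer"), and section 4.3 bars live vaccines for 3 months after abatacept stops. Neither is a contraception standard, so no shortfall is computed against them.

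**The window concerns a pregnant participant, not a male participant's partner.** This is true. Section 11.1 asks for partner pregnancies to be reported but attaches no half-life window to them. The case for one end date for both sexes rests on item 12, which already binds both.

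**Few people are affected and safeguards exist.** Pregnancy is excluded at entry, tested for at scheduled visits, leads to permanent discontinuation and is followed to outcome. This lowers the severity but does not supply the missing end date.

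**Conclusion.** The point holds as a gap in the protocol text: birth control is required to an undefined end with no post-dose interval, while section 11.1 counts exposure for at least 5 half-lives. Even on the more generous 30-day reading, cover falls short for any half-life above 6 days. On the closing-visit reading the threshold is about 1.4 days, or lower if the last dose is nearer the visit.

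The conclusion rests on weekly dosing to the end of each phase, and on item 12 being read without help from the consent form or the Brochure. The length of the gap in days cannot be stated without the half-life, and the number of participants concerned is unknown, at most 20. The severity is modest. Sample size, power and the primary analysis are untouched.

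**What to change.** Amend section 4.1, item 12, to require birth control from first dose through at least 5 half-lives after the last dose of study drug, whether that dose is randomized or open-label. State the interval in days, using the half-life in the Investigator's Brochure. Put the same number in sections 9.1 and 11.1, and restore the missing word in 9.1. Align the consent form if it says something different.

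The cost is wording in three protocol sections and possibly the consent form, with no new visits. The downside is a modestly longer contraception commitment. Because Phase I is blinded, it would also bind placebo participants who do not continue to open label.
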